8.2. Setting

Patients who were California or Louisiana residents in the HealthVerity claims database will be defined using the following hierarchical definition:

- Persons who have their enrollment file record indicating a patient location of California or Louisiana in HealthVerity claims enrollment file.
- 2. Persons who have a patient state location other than California or Louisiana in HealthVerity claims enrollment but have one or more records in the California or Louisiana Immunization Registry. Examples include people who previously lived in Texas but moved to California and received a vaccine, or persons who crossed state lines for a vaccine and remain in their non-California state in claims data.

XBB vaccinations will be enumerated using the following hierarchical definition:

- Any person in HealthVerity claims data who has a record in the California/Louisiana Immunization Registry with a CVX code indicating having received the BNT162b2 XBB.1.5 monovalent mRNA vaccine will be considered vaccinated 14 days after registry event date.
- Any person in HealthVerity claims data who does not have a record in the California/Louisiana Immunization Registry but has a pharmacy claim with an NDC code indicating a BNT162b2 XBB.1.5 monovalent mRNA vaccine dose will be considered vaccinated 14 days after claim date.
- 3. Any person in HealthVerity claims data who does not have a record in the California/Louisiana Immunization Registry and does not have a pharmacy claim with an NDC code indicating a BNT162b2 XBB.1.5 monovalent mRNA vaccine dose but has a medical claim with a CPT code indicating a BNT162b2 XBB.1.5 monovalent mRNA vaccine dose will be considered vaccinated 14 days after claim date.
- 4. Any person in HealthVerity claims data who does not have a record in the California/Louisiana Immunization Registry, does not have a pharmacy claim with an NDC code indicating a BNT162b2 XBB.1.5 monovalent mRNA vaccine dose and does not have a medical claim with a CPT code indicating a BNT162b2 XBB.1.5 monovalent mRNA vaccine dose will be considered BNT162b2 XBB.1.5 unvaccinated.

BA.4/5 vaccinations will be enumerated in the same manner as XBB.1.5. For influenza, herpes zoster and pneumococcal vaccinations, Pfizer has not yet licensed these specific California/Louisiana state registries; instead, we will rely wholly on NDC and CPT codes in administrative claims.

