8.3. Variables

TABLE 3. EXPOSURE VARIABLES

Variable	Data source(s)	Operational definition
BNT162b2 XBB.1.5 mRNA vaccine after FDA authorization date and 14 or more days	California/Louisiana Immunization Registry as well as HV Claims	Vaccines will be enumerated as per section 8.2. Date of vaccination will be used to assess time-based inclusion/exclusion criteria.
BNT162b2 BA.4/5 mRNA vaccine after FDA authorization date and 14 or more days	California/Louisiana Immunization Registry as well as HV Claims	Vaccines will be enumerated as per section 8.2. Date of vaccination will be used to assess time-based inclusion/exclusion criteria.
Influenza vaccine	HV Claims	Identified using NDC or CPT code

TABLE 4. OUTCOME VARIABLES

Variable	Data source(s)	Operational definition
COVID-19 diagnosis	HV Claims	Any encounter regardless of diagnosis position or setting with ICD-10-CM code: U07.1
COVID-19 hospitalization	HV Claims	Inpatient encounter at an acute care facility with ICD-10-CM code: U07.1 "COVID-19" listed in any diagnosis position
COVID-19 emergency department visit	HV Claims	Emergency department visit with ICD-10-CM code: U07.1

Variable	Data source(s)	Operational definition
COVID-19 outpatient encounter	HV Claims	Outpatient encounter with ICD-10-CM code: U07.1
COVID-19 critical illness	HV Claims	Intensive care unit [ICU] admission, mechanical ventilation, or inpatient death
All-cause mortality	HV Mortality Database	HealthVerity ID in Mortality Database
Non-COVID-19 respiratory infections (pneumonia, RSV, rhinovirus, antibiotic prescriptions)	HV Claims	Any encounter regardless of setting with ICD-10- CM code for diagnosis or NDC codes for antibiotics (Codes in Annex)
Hospitalization length of stay (days)	HV Claims	Date of service end – date of service
ICU admission	HV Claims	As per HealthVerity's suggestion, ICU related services/inpatient stays will be found on Institutional claims, and can be identified using revenue codes (codes in Annex).
Invasive ventilation	HV Claims	CPT, HCPCS and ICD-10 (codes in Annex)
Cost of hospitalization	HV Claims	Using HealthVerity's "Proxy Financial Algorithm", based on CMS Medicare prospective payment system fee schedules
Influenza diagnosis	HV Claims	Any encounter regardless of setting with ICD-10- CM code: J09-J11
Influenza hospitalization	HV Claims	Inpatient encounter with ICD-10-CM code: J09- J11 listed as in any diagnosis position

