Inpatient admission(s) prior to index	HV Claims	Number of inpatient admission(s) in 180 days prior to index
Telehealth visits prior to index	HV Claims	Number of telehealth encounters (CPT: 99201- 99215) in 180 days prior to index
Number of documented SARS-CoV-2 tests in the 180 days prior to index	HV Claims	Number of visits in any setting with CPT: 86408, 86409, 0225U, 0226U
Prior post-COVID-19 conditions	HV Claims	Using all-available lookback data, any encounter regardless of setting with ICD-10-CM U09.9 "Post-COVID-19 condition"
For aim 5 only (coadministration): Number of documented influenza tests in the 180 days prior to index	HV Claims	Number of visits in any setting with CPT: 87400
For aim 5 only (coadministration): Lipid and/or HbA1C labs in the 180 days prior to index	HV Claims	Encounter with CPT: A56686. These labs were selected as potential measures of health system usage, as people who monitor their lipids or blood glucose may share some behaviors as vaccinations. We are able to incorporate this in propensity score adjusted analyses (aim 5) but not analyses with direct adjustment (aim 1, 2 and 4), given the need for smaller sets of covariates.
For aim 5 only (coadministration): vaccine administration setting	California /Louisiana Vaccine Registry	As pharmacy, doctor's office, or other.

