8.4.1. California and Louisiana Immunization Registry

The California Immunization Registry is run by the California Department of Public Health and collects nearly all records of COVID-19 vaccinations administered in the state of California. Sites exempted from reporting are the Department of Defense, Veterans Affairs and Indian Health Services; these sites are not included in the registry and will not contribute to any objective herein. In the July 2023 delivery of these data, there were 88 million COVID-19 vaccinations recorded for 32 million unique individuals. In this delivery, we identified 72.2% of persons had received at least two wild type vaccine doses (note: for non-immunocompromised persons over age 5 this represents the completion of primary vaccination series), with California's state dashboard²⁶ reported 72.9%. Similarly, we identified 20.9% of persons in the registry having received at least one bivalent vaccine dose, as compared to California state's estimate of 21.2%.

Data include a unique HealthVerity person identification code, vaccination event date and Clinical Vaccines Administered (CVX) code. CVX codes are unique to brand and formulation of vaccine.

Data is linked using HealthVerity's tokenization software, whereby specific patient identifiers are passed through the software and a de-identified patient ID is assigned. The same tokenization process is applied to closed claims sourced by HealthVerity, and patients can thus be linked across data sources. The tokenization process occurs outside of Pfizer, no personal identifying information will be transferred, and Pfizer will only have access to de-identified data. The data comply with Health Insurance Portability and Accountability Act (HIPAA) regulations.

The Louisiana Vaccine Registry is structured and accessed in the same way as California.

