8.7. Data Analysis

Detailed methodology for summary and statistical analyses of data collected in this study will be documented in a statistical analysis plan (SAP), which will be dated, filed, and maintained by the sponsor. The SAP may modify the plans outlined in the protocol; any major modifications of primary endpoint definitions or their analyses would be reflected in a protocol amendment.

[figure not shown]
Throughout, we will use missing data indicator variables for absence of values in categorical variables (such as insurance payor) and exclude persons with missing data in continuous variables (age). Using indicator variables rather than imputation allows for the missing data patterns to be mathematically informative. Variables with data delivered of strings as 'Missing' or 'Unknown' values will be reported and analyzed as separate categories and included in the totals.

All steps will be completed using SAS version 9.4 and/or R.

8.7.1. Aim 1

To evaluate the VE of BNT162b2 formulations in non-pregnant, non-immunocompromised adults against medically attended COVID-19, mortality and healthcare resource utilization by age and adapted vaccine formulation.

Figure 1. Aim 1 study design

Exposure: time-varying exposure. All persons will be considered unvaccinated from FDA date of vaccine authorization/approval until, where applicable, 13 days after receipt of vaccine. In order to allow for time after dose for meaningful immunologic protection to accrue, persons will be considered vaccinated 14 days after vaccination (i.e. patients will be censored from the unvaccinated group). 20,21

For XBB.1.5 vaccine: FDA approval date 11 September 2023²

In the event that XBB uptake is low, we will instead examine BA.4/5 VE. For BA.4/5 vaccine: FDA emergency use authorization date 31 August 2022⁴

Note: this aim pertains to adults only, and therefore does not require age-specific EUA dates.

Follow-up time: From date of FDA authorization/approval until the outcome of interest, or are censored at the first of the following: 6 months of follow-up, end of medical and/or pharmacy enrollment, receipt of a non-Pfizer BioNTech vaccine or receipt of a second BNT162b2 COVID-19 vaccine dose.

Primary outcome:

A COVID-19-related encounter, regardless of setting

Secondary outcomes:

- An outpatient encounter with ICD-10-CM U07.1 "COVID-19" code

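### Aim 5, co-administered versus influenza alone: administration setting comes only from the registry, so influenza-only recipients have no value and, if the field exists, positivity fails in this contrast

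*Protocol*

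**What the plan says.** The relevant statements are in different parts of the protocol.

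- **The covariate.** Table 5 (Section 8.3) includes "For aim 5 only (coadministration): vaccine administration setting", sourced from the California/Louisiana Vaccine Registry and coded "As pharmacy, doctor's office, or other". It has no claims source and no level for people without a registry record. It does not say which dose the setting refers to.
- **Influenza doses.** For influenza and two other vaccines, Section 8.2 states that "Pfizer has not yet licensed these specific California/Louisiana state registries; instead, we will rely wholly on NDC and CPT codes in administrative claims". Table 3 agrees: "Identified using NDC or CPT code".
- **XBB.1.5 doses.** Section 8.2 looks in the registry first. Claims are used for a person who "does not have a record in the California/Louisiana Immunization Registry but has a pharmacy claim with an NDC code", and then for medical claims.
- **Registry content.** Section 8.4.1 lists a person identifier, "vaccination event date and Clinical Vaccines Administered (CVX) code". Setting is not in that list.
- **Missing values.** Section 8.7: "we will use missing data indicator variables for absence of values in categorical variables".
- **Use in the analysis.** Under Section 8.7.6, the stabilized weights model the probability of co-administration given the Table 5 covariates. Weights are capped at the 1st and 99th percentiles if necessary. Variables with a standardized mean difference (SMD) above 0.10 after weighting enter the outcome model. Co-administration is compared separately with COVID-19 vaccine alone and with influenza vaccine alone.

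The SAPs supplied cover Aims 1, 2 and 3B. None covers Aim 5.

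**The concern.** An influenza-only recipient has no COVID-19 dose on the index date, and the influenza dose is not in the licensed registry data. There is therefore nowhere for an index-dose setting to come from, and the person goes into the missing category. A co-administered recipient with a registry XBB.1.5 record would have a setting. The covariate then records mainly which arm a person is in, not where the vaccine was given.

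Weighting needs people from both arms at every covariate level used. Here the recorded-setting levels contain no influenza-only comparators. What is at stake is the adjusted risk ratio for influenza outcomes, one of Aim 5's two main summary measures, which the protocol intends for evaluating non-inferiority. The contrast with BNT162b2 alone does not have this structural gap, because both its arms have COVID-19 doses that are looked up in the registry first.

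**Working it through.** The documents give no sample size or precision figure for Aim 5, so there is no plan figure to reproduce.

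**Assumed inputs, none given in the documents**
- p: share co-administered among co-administered plus influenza-only people, 0.2 to 0.4.
- f: share of co-administered people whose XBB.1.5 dose is found only in claims, 0 to 20%.
- The registry has a setting field, filled for registry doses. Setting refers to the index dose. The propensity model is fitted within the contrast.

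**Propensity scores on this covariate**
- Setting recorded: only co-administered people, so e = 1.
- Setting missing: e = pf / (pf + 1 − p).

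**Stabilized weights**, p/e for co-administered and (1 − p)/(1 − e) for influenza-only:
- co-administered, registry: p
- co-administered, claims only: (pf + 1 − p)/f
- influenza-only: pf + 1 − p

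**Case f = 0 (complete separation).** Fitted scores go to 1 and 0. Weights are p for every co-administered person and 1 − p for every influenza-only person, e.g. 0.3 and 0.7. A constant cancels within each arm, so the weighted risk ratio equals the crude one. Percentile capping changes nothing.

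**Case f > 0 (quasi-complete separation), p = 0.3**

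| Quantity (co-administered arm) | f = 1% | f = 10% |
|---|---|---|
| Weight, claims-only person | (0.003 + 0.7)/0.01 = 70.3 | (0.03 + 0.7)/0.1 = 7.3 |
| Weight, registry person | 0.3 | 0.3 |
| Share of arm's weight on claims-only people, m = 1 − p(1 − f) | 70.3% | 73.0% |
| Effective sample, 1/[(1 − f)p² + m²/f] | 1/(0.089 + 49.42) = 2.0% | 1/(0.081 + 5.329) = 18.5% |
| SMD of the missing indicator, (1 − m)/√(m(1 − m)/2) | 0.92 | 0.86 |

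The weighted proportion with setting missing is m in the co-administered arm and 1.0 in the influenza-only arm. For p from 0.2 to 0.4 and f from 1% to 20%, the SMD runs from 0.62 to 1.15. It is always above 0.10, so setting would go into the outcome model.

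**Simulation** (200,000 people, one confounder with SMD about 0.5 before weighting, true risk ratio 1.0, p = 0.2 and 0.4; weighting only, no outcome-model adjustment)

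| Propensity model | Weighted risk ratio | Confounder SMD |
|---|---|---|
| Setting included, f = 0 | 1.33 and 1.37 (equal to crude) | 0.49 and 0.50 |
| Setting included, f = 1% to 20%, uncapped | 1.00 to 1.12 | 0.08 to 0.20 |
| Setting included, f = 1% to 20%, capped | 1.09 to 1.37 | 0.20 to 0.49 |
| Setting left out, uncapped | 0.97 to 1.03 | at most 0.005 in size |

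In the uncapped runs with setting included and f > 0, the effective sample of the co-administered arm was 1% to 35% of its size. With setting left out it was 85% to 92%. These sizes depend on the assumed p, f and confounder strength. The absence of influenza-only people with a recorded setting does not.

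**The case against.** **The plan has diagnostics and a fallback.** Section 8.7.6 looks at the weight distribution, checks SMDs before and after weighting, and adjusts the outcome model for anything above 0.10. This has force. Other confounders left unbalanced would enter the outcome model, so the simulated risk ratios above, which omit that step, are not predictions of the final estimate. The same rule would also enter setting, which nearly coincides with exposure. And when f = 0 the weights themselves look unremarkable; only the SMDs show the problem.

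**Setting may not exist in the registry data.** If the field is absent, setting is missing for everyone, the indicator is constant and nothing separates. The gap in Section 8.4.1 is thus a separate availability question. It is not evidence for the positivity failure, which requires the field to exist.

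**Setting might mean an earlier COVID-19 dose, or influenza-only people might be coded as other.** The first would be a different variable, and nothing in the text defines it. The second would still leave the pharmacy and doctor's-office levels without influenza-only comparators.

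**An Aim 5 SAP may resolve it.** Section 8.7 allows a SAP to modify the plan. None for Aim 5 is among the documents, so the protocol text is what can be judged.

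**Stronger inferences that the documents do not support.** A reader might conclude that the weights must be extreme or undefined. That needs some claims-only XBB.1.5 doses; with none, the weights are constant and simply adjust for nothing. A reader might also put missingness at about 100% against 0%. The first figure follows from the definitions. The second does not, because the documents report neither how complete setting is nor how many XBB.1.5 doses are found only in claims.

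**Conclusion.** The point holds for one of the two contrasts in an exploratory aim: co-administered versus influenza alone. As written, and provided the registry supplies setting for the index dose, that propensity model violates positivity by construction. The result ranges from no confounding control by weighting (f = 0) to an arm dominated by a few claims-only people: 70.3% of the weight on 1% of the arm, or 73.0% on 10%, at an assumed p = 0.3. Capping does not cure it, and the SMD rule would add a covariate nearly collinear with exposure.

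A reader might extend this to all of Aim 5, but the contrast with BNT162b2 alone is not affected in this way. The size of any bias in the final risk ratio cannot be stated from the documents.

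**What to change.** In Table 5 and the Aim 5 SAP:

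1. Confirm whether the licensed registry data contain a setting field, and state which dose it describes.
2. For the influenza-alone contrast, either leave setting out of the propensity model, or define it in both arms from the influenza claim (pharmacy NDC claim versus medical CPT claim). Co-administration requires a same-day influenza dose and influenza doses come only from claims, so everyone in this contrast has such a claim.
3. For the contrast with BNT162b2 alone, keep the registry setting if it is available. Claims-derived setting should not be imposed on all arms: Section 6 explains that roster-billed doses generate no individual claim. Registry-only BNT162b2-alone recipients could then lack a setting while co-administered people always have an influenza claim.

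The cost is a wording change and a separate covariate list for each contrast; claim type is already in the data. The downside is a coarser setting variable, or no adjustment for setting, in that one model.

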8.4. Data Sources

This study will use vaccination data from the California/Louisiana Immunization Registry linked to closed claims for patients in California sourced from HealthVerity.

8.4.1. California and Louisiana Immunization Registry

The California Immunization Registry is run by the California Department of Public Health and collects nearly all records of COVID-19 vaccinations administered in the state of California. Sites exempted from reporting are the Department of Defense, Veterans Affairs and Indian Health Services; these sites are not included in the registry and will not contribute to any objective herein. In the July 2023 delivery of these data, there were 88 million COVID-19 vaccinations recorded for 32 million unique individuals. In this delivery, we identified 72.2% of persons had received at least two wild type vaccine doses (note: for non-immunocompromised persons over age 5 this represents the completion of primary vaccination series), with California's state dashboard²⁶ reported 72.9%. Similarly, we identified 20.9% of persons in the registry having received at least one bivalent vaccine dose, as compared to California state's estimate of 21.2%.

Data include a unique HealthVerity person identification code, vaccination event date and Clinical Vaccines Administered (CVX) code. CVX codes are unique to brand and formulation of vaccine.

Data is linked using HealthVerity's tokenization software, whereby specific patient identifiers are passed through the software and a de-identified patient ID is assigned. The same tokenization process is applied to closed claims sourced by HealthVerity, and patients can thus be linked across data sources. The tokenization process occurs outside of Pfizer, no personal identifying information will be transferred, and Pfizer will only have access to de-identified data. The data comply with Health Insurance Portability and Accountability Act (HIPAA) regulations.

The Louisiana Vaccine Registry is structured and accessed in the same way as California.

8.4.2. Health Verity's Administrative Claims Data

HealthVerity closed claims will be limited to approximately 19 million patients residing in California and approximately 3.8 million in Louisiana. Patients who were California/Louisiana residents in the HealthVerity claims database will be defined using the following hierarchical definition:

- Persons who have their most recent enrollment file record indicating a patient location of California or Louisiana in HealthVerity claims enrollment file.
- 2. Persons who have a patient state location other than California/ Louisiana in HealthVerity claims enrollment but have one or more records in the California/ Louisiana Immunization Registry. Examples include people who previously lived in Texas but moved to California and received a vaccine, or persons who crossed state lines for a vaccine and remain in their non-California state in claims data.

HealthVerity's description of their data is that they are generally representative of the age and sex distribution of the population. For our specific research context, samples created from HealthVerity claims also generally follow California's demographic patterns with respect to age & sex. However, there are several caveats to note. Our claims population is slightly more female and young people (particularly age 5-17) are overrepresented in our claims relative to other groups. Children under 5, and adults 65+, are slightly underrepresented.

The California subset of HealthVerity does not include patients in the Kaiser Permanente network. Insurers contributing to closed claims in both states include a mix of commercial payers, Medicare Advantage/Part C pains, and Medicaid Managed Care plans. Data elements include patient demographic information, inpatient/outpatient visit-level information such as diagnoses, procedures, and length of stay, hospital characteristics, and medication information. Owing to the nature of claims, the data represent the final set of diagnoses over the course of the hospitalization sent to the patient's insurer for reimbursement, with diagnosis prioritization assigned by clinicians or hospital staff. For inpatient encounters, the data will be assumed to represent the overarching events during hospitalization and may be less subject to rule out diagnosis codes than electronic health record data.

Death information is available and is sourced from over 40,000 public and private sources nationally. The coverage rate, estimated at over 90% of CDC reported deaths through present day, is based on the number of deaths in the Fact of Death Mortality Index compared to the number of deaths reported by the CDC. Due to HIPAA privacy restrictions, date of death is reported as month and year. Cause of death is not available.

